Primary Objective:	Determine the safety of HB-adMSCs as determined by infusional toxicity of the cell product.
Secondary Objectives:	Obtain treatment effect estimates of HB-adMSC infusion on global gray and/or white matter as well as structural integrity of GM and WM regions of interest in the corpus callosum and corticospinal tracts as measured by fractional anisotropy (FA) and mean diffusivity (MD) in specific regions known to correlate with specific neurocognitive deficits in patients after neurological injury.
Exploratory Objective:	Investigate if HB-adMSC infusion reduces the neuroinflammatory response to injury.
Study Design	Non-Randomized, Phase 1/2a study of three infusions of autologous HB-adMSCs (2×10^8 total cells per dose) administered over a 6wk. period with 14 day intervals between infusions.
Sample Size	A maximum of 24 patients.
Inclusion Criteria	
 1. Adults between 18 and 55 years of age. 2. Documented functional neurological damage to the central nervous system from closed head trauma unlikely to improve with present standard of care approaches. 3. A Glasgow Outcome Scale-Extended (GOS-E) score >2 and ≤ 6. 4. Onset or diagnosis of the injury or disease process greater than 6 months. 5. Ability to obtain consent from the subject or their legally authorized representative (LAR). 6. Ability to communicate in English or Spanish (required for validated neurocognitive outcome testing).
Exclusion Criteria	
 1. Known history of: 
 a) intellectual deficiency or psychiatric conditions likely to invalidate our ability to assess changes in cognition or behavior, b) recently treated infection, c) renal disease or altered renal function (screening eGFR > 60 mL/min/1.73m²), d) hepatic disease or altered liver function (screening SGPT > 150 U/L or T. Bilirubin >1.3 mg/dL), e) cancer, f) immunosuppression (screening WBC $< 3,000$ cells/ml), g) HIV+, h) chemical or ETOH dependency that in the opinion of the investigator would preclude participation in the study, i) acute or chronic lung disease requiring significant medication, oxygen supplementation, or mechanical ventilation, j) bleeding disorders including immune-mediated heparin-induced thrombocytopenia, k) known sensitivity to heparin, Lovenox, and pork products, l) individuals with mechanical prosthetic heart valves.m) individuals who have received a stem cell treatment. 2. Normal brain CT/MRI exam. 3. Spinal deformity, spinal surgery (including repeated epidural or spinal punctures), or complete spinal cord injury diagnosed by CT/MR or clinical exam.

	
 4. Diagnosed with a genetic or metabolic disorder related to the neurologic condition. 5. Other acute or chronic medical conditions that, in the opinion of the investigator, may increase the risks associated with study participation. 6. For women of child bearing potential, a positive pregnancy test at the screening visit or, for both women and men, unwillingness to comply with acceptable methods of birth control during the study. 7. Concurrent participation in an interventional drug or device study. 8. Inability to undergo the diagnostic tests (PET/DT-MRI) or unwilling/unable to cooperate with the diagnostic tests and outcome assessments. 9. Unwilling or unable to return for follow-up study visits. 10. Individuals planning to receive a vaccination two weeks before the brain imaging visits or planning to receive a vaccination two weeks before or after a stem cell infusion visit.
Safety Monitoring and Follow-Up	Subjects will be monitored and assessed for infusion related toxicity for the first 4hr. after the infusion and by telephone 24hr. after each infusion. Safety assessments will be conducted at the study follow-up clinic visits 6 and 12 months, and 2 years (telephone call) after the last HB-adMSC infusion, or more frequently if infusion related adverse events are suspected.
Statistical Analyses	The data will be analyzed using general linear mixed models (GLMMs) to estimate differences across time points (pre- and post-treatment).
Stopping Rules	
The stopping rules listed below will trigger cessation of enrollment and potential study closure pending a comprehensive DSMB safety review.
 
 1. Any infusion related death. 2. An infusion related, sustained (over 3 minutes) episode of hypoxia (SaO₂ of less than 80%) or the new requirement for mechanical ventilation. 3. Grade 4-5 CNS cerebrovascular ischemia event or Grade 4-5 seizure event as defined in the NCI CTCAE v4.0 occurring within 48 to 72 hours of the infusion. 4. Any Grade 4-5 Adverse Event as defined in the NCI CTCAE v4.0 and determined to be temporally related to the HB-adMSC infusion by the Medical Safety Monitor and/or DSMB.

ABBREVIATIONS

adMSCs-Adipose Derived Mesenchymal Stem Cells
ADL-Activities of Daily Living
AE-Adverse Event
ANAM-Automated Neuropsychological Assessment Metrics
ARDS-Adult Respiratory Distress Syndrome
CAT-Calibrated Automated Thrombogram
CBC-Complete Blood Count
CCI-Controlled Cortical Impact
CD142-Tissue Factor or Platelet Tissue Factor
CFU-Colony Forming Unit
CGMP-Current Good Manufacturing Practices
CFR-Code of Federal Register
CMP-Complete Metabolic Panel
CNS-Central Nervous System
CRF-Case Report Form
CRO-Contract Research Organization
CRU-Clinical Research Unit
CSF-Cerebral Spinal Fluid
CTCAE-Common Terminology Criteria for Adverse Events
CXR-Chest X-Ray
DSMB-Data Safety Monitoring Board
DTI-Diffusion Tensor Imaging
DVT-Deep Vein Thrombosis
EMR-Electronic Medical Record
ESC-Embryonic Stem Cells
ETOH-Ethanol/Alcohol
F-Fibroblast
FA-Fractional Anisotropy
FDA-Food and Drug Administration
GCP-Good Clinical Practice
GCS-Glasgow Coma Scale
GLMM-Generalized Linear Mixed Model
GM-Gray Matter
GOAT-Galveston Orientation and Amnesia Test
GOS-E-Glasgow Outcome Scale - Extended
HB-adMSC's-Hope Biosciences' Autologous Adipose-Derived Mesenchymal Stem Cells
HIPAA-Health Insurance Protection and Portability Act
HMRI-Houston Methodist Research Institute
HPA-Hypothalamo-Pituitary-Adrenocortical
HTLV- Human T-Lymphotropic Virus
IDO-Indoleamine 2,3-dioxygenase
IND-Investigational New Drug
INR-International Normalized Ratio
iPS Cells-Induced Pluripotent Stem Cells
IV-Intravenous
IRB-Institutional Review Board
LAR-Legally Authorized Representative
LPS-Lipo-Polysaccharide
MAPC-Multipotent Adult Progenitor Cells
MD-Mean Diffusivity
MHH-Memorial Hermann Hospital
MNC-Mononuclear Cells

MSC-Mesenchymal Stem Cell

MSM-Medical Safety Monitor

MRI-Magnetic Resonance Imaging

NCI-CTCAE-National Cancer Institute-Common Terminology Criteria for Adverse Events

NIDRR-National Institute on Disability and Rehabilitation Research

NIH-National Institutes of Health

NINDS-National Institute of Neurological Disorders and Stroke

NSC-Neural Stem Cells

PBS-Phosphate Buffered Saline

PCP-Primary Care Provider

PE- Pulmonary Embolism

PET-Positron Emitting Radionuclide

PI-Principal Investigator

PMN-Polymorphonuclear Leukocytes

PT-Prothrombin Time

PTT-Partial Thromboplastin Time

QA-Quality Assurance

QC-Quality Control

SAE-Serious Adverse Events

SQ-Subcutaneous

TBI-Traumatic Brain Injury

TSPO-Translocator Protein

VFT- Verbal Fluency Test

VOI-Volume of Interest

VTE-Venous Thromboembolism

WBC-White Blood Count

WM-White Matter

WOCBP-Women of Childbearing Potential

**A Clinical Trial to Determine the Safety and Efficacy of Hope
Biosciences Autologous Mesenchymal Stem Cell Therapy for the Treatment
of Traumatic Brain Injury and / or Hypoxic-Ischemic Encephalopathy**

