3.6 Visits #3 thru 5: HB-adMSC Infusions

The infusion visits will be conducted in the CRU. Subjects will receive a total of 3 infusions (2×10^8 total cells per dose) administered over a 6 week period with 14 day intervals between infusions (+/- 3 days). The volume of each infusion will be 250mL infused over a 1hr. period (+/- 5 min.) at a rate of 4-5mL per minute.

At each infusion visit, the subject will undergo the following study procedures:

1. Interval H&P update (*detailed neuro exam if indicated from interview and physical exam, current medications and recent vaccinations*),
2. Confirmation the subject started prophylactic Lovenox injections and review of the Lovenox medication logs at follow-up visits,
3. A pregnancy test will be repeated for female subjects of child bearing potential (if applicable),
4. Vital signs (Heart Rate, BP, Resp., Temp., SpO₂),
5. Insertion of a peripheral IV line,
6. Blood sample for clinical labs (CBC with diff., CMP, coagulation and renal function panels),
7. Benadryl and Solumedrol will be given as pre-meds before the infusion. The dose for both drugs will be 25mg for subjects <100kg. or 50mg for subjects $\geq 100\text{kg}$.
8. A “time out” verification of patient/consent/procedure/cell product will be performed,

9. The HB-adMSC infusion will be given by through the peripheral IV,
10. The subject will then be monitored for a minimum of 4hr.

Vital signs will be continuously monitored during the infusion and recorded at 15 minute intervals. Vital signs will be recorded at the end of the infusion and then every 15 minutes x 4 (1st hour), and then every 30 minutes x 4 (next 2 hours), and then every hour until discharge from the CRU, or more frequently if clinically indicated. A chest x-ray may be obtained if clinically indicated to assess pulmonary AE/SAE's. The subject will be contacted by telephone 24hr. after each infusion visit to determine if adverse events have occurred. Each infusion visit is expected to take around 6 hours to complete.

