3.7 Visit #6: Six Months Post-Infusion

Safety and outcome assessments will be conducted in the CRU and at the HMRI 6 months from the last HB-adMSC infusion. The visit will include:

1. Interval H&P update,
2. Vital signs (Heart Rate, BP, Resp., Temp., SpO₂),
3. Blood sample for clinical labs (CBC with diff., CMP, coagulation and renal function panels) and neuro-inflammatory biomarkers,
4. A pregnancy test will be repeated for female subjects of child bearing potential (if applicable),
5. PET/DT-MRI,
6. Neurocognitive/functional outcome assessments.

The visit is expected to take about 8 hours and may require two days to complete the assessments and brain imaging.

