3.10 Participant Satisfaction Survey

Subjects or their care provider will be invited to complete an anonymous satisfaction survey in REDCap. The survey results will be used for the development of future clinical research studies requiring community based participatory research (CBPR) activities with the goal of improving research recruitment and retention.

Table 1a: Study Procedures

Study Procedures	Visit 1 Screening & Consent	Visit 2 Baseline Imaging	5 to 7 weeks for HB-AdMSC Processing	Visit 3 Inf. #1	Visit 4 Inf. #2	Visit 5 Inf. #3	Visit 6 6 Mo. Post-Inf. (+/- 21 Days)	Visit 7 1 Yr. Post-Inf. (+/- 21 Days)
Visit Location	CRU	HMRI		CRU	CRU	CRU	CRU / HMRI	CRU
Review of Medical History	X						X	X
Consent	X	X		X	X	X	X	X
Physical and Neuro Exam ¹	X	X		X	X	X	X	X
Vital Signs ²	X	X		X	X	X	X	X
Clinical Lab Evaluations ³	X			X	X	X	X	X
Research Blood Sample for TSPO Genotype	X							
Research Blood Sample for Neuroinflammatory Biomarkers	X						X	X
Neurocognitive/Functional Outcome Tests	X						X	X
Adipose Tissue Extraction ⁴ (Hope Bio. Clinical Facility)		X						
Prophylactic Lovenox ⁵				X	X	X		
Pre-Infusion Medications ⁶				X	X	X		
HB-AdMSC Infusion with 4hr. Observation ⁷				X	X	X		
Safety/Toxicity Assessments ⁸		X		X	X	X	X	X
Chest X-Ray (AP, Single View) ⁹	X							X
PET / DT-MRI Imaging ¹⁰		X					X	

1. Detailed Neuro exam optional on infusion visits based on physical exam and interval changes. **2.** Vital Signs: at baseline after consent, before and after the stem cell infusion, then q. 15min x 4, (1st hour), q. 30min. x 4 (next 2hrs.) then hourly until discharge, at follow-up visits, or more frequently if indicated.

3. CBC with diff, metabolic (CMP), coagulation and renal function panels, hCG (if applicable). **4.** Performed under Hope Biosciences IND #18388

procedures. **5.** Seven day course of prophylactic SQ Lovenox (40mg QD) beginning the day before each infusion visit. Subjects will receive a reminder telephone call the day before beginning each round of Lovenox. Lovenox will not be required for subjects already taking an anticoagulant. **6.** Benadryl

/Solumedrol (25mg for subjects <100kg or 50mg for subjects \geq 100kg.) I.V. 30 min. before infusion. **7.** Infusion given over a 1hr period (+/- 5 min.) with 14-day interval between study infusions (+/- 3 days). **8.** Assessment by telephone call 24hr. after each cell infusion and 24mo. after the last cell infusion. **9.**

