4. RISKS

4.1 Respiratory Risks:

A concern exists regarding the intravenous infusion of large, adherent cells in a concentrated manner into a patient with a dysregulated systemic inflammatory response syndrome. A potential risk is amplification instead of diminution of the post-trauma pro-inflammatory response that typically manifest as exacerbation of respiratory failure or ARDS. Alternatively, the infusion could initiate a VTE event with subsequent cardiopulmonary sequelae of respiratory failure and/or right heart strain/failure. Infused cells will be evaluated for CD142 expression (cell number and intensity) and evaluated via in vitro thromboelastography for pro-coagulant activity. We plan to monitor oxygen saturation, and respiratory rate/work of breathing for the first 4 hours post-infusion. Chest x-rays will be obtained at baseline and the final study visit or more frequently if clinically indicated. We will re-examine the patient for VTE events (clinical exam, oxygen saturation) at each follow-up visit.

4.2 Hepatic Risks:

The reticuloendothelial system can sequester immature blood elements, theoretically resulting in hepatic injury. An acute elevation of the AST/ALT hepatic enzymes $> 900 \text{ U/dl}$ post-infusion will be considered an infusion related adverse event. This level is based upon the organ system scoring definitions for moderate hepatic failure and corresponds to the CTCAE v4.03 Grade 4 adverse event. It is unlikely that "end vessel" microthrombosis would occur in the liver due to the dual blood supply of the liver and the lung is the first pass organ. A comprehensive metabolic panel including AST/ALT will be drawn at each follow-up visit.

4.3 Neurologic Complications:

The patient's acute neurologic status will be evaluated at each study visit. A grade 4-5 CNS cerebrovascular ischemia event or Grade 4-5 seizure event as defined in the CTCAE v4.03 occurring within 4 hours of HB-adMSC infusion will be considered an infusion related adverse event. Other changes temporally related to HB-adMSC infusion (those events occurring within 48 to 72 hours of infusion) will be considered associated with the protocol and recorded as an adverse event.

4.4 Coagulation Cascade:

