A coagulation panel will be obtained to include PT, PTT, (INR), FSP/D-Dimer, PLT thrombo-elastography, CAT, and CD142. Patients will also be monitored for the development of venous thrombo-embolic events (see pulmonary monitoring above) as well as for the development of clinical deep vein thrombosis (limb swelling, tenderness, discoloration). To minimize the risk of DVT or PE, prophylactic Lovenox SQ injections (40 mg once a day) will be given for 7 days beginning the day before each infusion visit. Lovenox will not be administered to subjects already taking an anticoagulant.

4.5 Pregnancy:

Studies to assess the reproductive and developmental toxicity of HB-adMSC's have not been conducted at this time. Women of child bearing potential (WOCBP) and men (if their sexual partners are WOCBP) must use an effective form of birth control throughout the study period. Highly effective birth control methods include sexual abstinence, surgical sterilization (hysterectomy, tubal ligation, vasectomy, etc.), hormonal contraceptives associated with inhibition of ovulation, intrauterine device, or intrauterine hormone -releasing system. Post-menopausal is defined as having no periods for at least 12 months without another medical cause.

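### After infusion 3 the only scheduled contact between discharge and the 6-month visit is a 24-hour call, so later infusion-related events rest on spontaneous report or recall about six months on

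*Protocol*

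**What the plan says.** Protocol section 3.6 sets the acute follow-up of every infusion. On site, "The subject will then be monitored for a minimum of 4hr". After discharge, "The subject will be contacted by telephone 24hr. after each infusion visit to determine if adverse events have occurred". The Synopsis (Safety Monitoring and Follow-Up) agrees: "Subjects will be monitored and assessed for infusion related toxicity for the first 4hr. after the infusion and by telephone 24hr. after each infusion". It also allows extra assessments when an infusion-related event is suspected. Footnote 8 to Tables 1a and 1b lists two kinds of safety call and no others: "Assessment by telephone call 24hr. after each cell infusion and 24mo. after the last cell infusion".

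What comes next depends on the infusion. Infusions 1 and 2 are followed 14 ± 3 days later by the next infusion visit. Section 3.6 gives that visit an interval history and examination, vital signs including SpO₂, and clinical labs, and both tables mark a safety assessment there. After infusion 3, section 3.7 places the next visit "6 months from the last HB-adMSC infusion", and the tables allow ± 21 days.

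The protocol also says over what period it expects trouble:

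- Section 4.3 treats changes temporally related to the infusion ("those events occurring within 48 to 72 hours of infusion") as associated with the protocol.
- Stopping rule 3 in the Synopsis applies 48 to 72 hours to Grade 4-5 CNS ischemia and seizure. Section 4.3 applies 4 hours to those same events.
- Section 4.4 says prophylactic Lovenox "will be given for 7 days beginning the day before each infusion visit", except in subjects already on an anticoagulant.
- Section 4.1, on VTE: "We will re-examine the patient for VTE events (clinical exam, oxygen saturation) at each follow-up visit".
- Section 3.5 has subjects hand in each Lovenox log at the following study visit.

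**The concern.** The primary objective is safety, judged by infusional toxicity. The protocol itself names VTE as a risk, gives prophylaxis against it for several days after each infusion, and counts neurologic changes as infusion-associated well beyond 24 hours. The one scheduled contact after discharge comes before any of those periods has ended.

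For infusions 1 and 2, a visit about two weeks later catches up, so the cost is delay. For infusion 3 nothing does so for about six months. The first scheduled VTE re-examination after that infusion, and the first review of the third Lovenox log, both fall at the 6-month visit. By then a transient or lower-grade event may be forgotten or misdated. All subjects enter with GOS-E 3 to 6, and consent through an LAR is permitted, so unaided recall over that interval is a weak source. Onset dates matter because attribution to the infusion turns on timing.

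**Working it through.** The plan gives no figure to reproduce here: N = 24 is stated without a power calculation. The check is calendar arithmetic, with infusion = day 0.

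**Inputs.** Call at 24 h (section 3.6, footnote 8). Infusion interval 14 ± 3 days (section 3.6). Six-month visit ± 21 days (section 3.7, Tables 1a/1b). Lovenox for 7 days from day −1 (sections 3.5, 4.4). Event window 48 to 72 h (Synopsis, section 4.3). 24 patients with 3 infusions each.

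**Gap to the next scheduled visit**

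- Infusions 1 and 2: 14 ± 3 = day 11 to 17. Counted from the 24-hour call, 10 to 16 days.
- Infusion 3: 365.25/2 = 182.6 days; 182.6 ± 21 = about day 162 to 204. Counted from the call, about 161 to 203 days.

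**Lovenox reminder call.** It is made the day before each course starts, which is 2 days before the infusion visit. After infusions 1 and 2 it falls on day 9 to 15 (11 − 2 to 17 − 2). It is not described as a safety check, and none follows infusion 3.

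**Event window left after the call.** The phrase 48 to 72 hours is ambiguous:

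- up to 72 h: 72 − 24 = 48 h, or 48/72 = 67%
- up to 48 h: 48 − 24 = 24 h, or 24/48 = 50%
- literally the band from 48 to 72 h: all of it

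On every reading, some of the window follows the call.

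**Prophylaxis left after the call.** Seven days from day −1 are days −1, 0, 1, 2, 3, 4, 5. Days +2 to +5, 4 of 7, follow the call.

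**Illustration (assumption, not in the documents).** Suppose a given type of event follows infusion 3 in a proportion p of 24 patients, and a fraction s of such events is ascertained. The chance of recording at least one is 1 − (1 − ps)^24:

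| p | s = 1 | s = 2/3 | s = 1/3 |
|---|---|---|---|
| 5% | 71% | 56% | 33% |
| 10% | 92% | 81% | 56% |

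The documents give no value for p or s. The table shows only that, with 24 patients, partial ascertainment can decide whether an event type is seen at all.

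**The case against.** Much can be said for the schedule as written.

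- A reader might infer that 67% of the window goes unobserved for all 72 infusions. The documents do not support that. Events at 24 to 72 hours after infusions 1 and 2 fall within the interval history taken at the next visit. The 67% also takes the upper end of an ambiguous phrase, and time after a call is not the same as events missed.
- A reader might infer that stopping rules 3 and 4 will be triggered months late. Both concern Grade 4-5 events, which are the least likely to stay unreported because they usually lead to hospital care. Late triggering is a worst case.
- A reader might infer that a comparison between infusions is biased. Neither Protocol section 8 nor the SAP plans one, and no formal hypothesis testing is foreseen.
- On section 4.3's 4-hour window, Grade 4-5 CNS events counted as infusion related are fully covered by on-site observation. That is correct, but stopping rule 3 uses 48 to 72 hours for the same events, so the 4-hour reading does not settle the matter.
- Caregivers are not ignored. They receive the Lovenox instructions, and the GOS-E is a caregiver interview at baseline, 6 and 12 months. The word subject in the call instruction may be generic.
- Section 6 appears only as an introduction and Appendix 3 is not included, so further contacts could be described there. Appendix 3 is said to cover only the first four subjects, however, and neither table shows extra contacts.

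These points narrow the concern to infusion 3 and to lower-grade or poorly dated events. They do not remove it. The allowance for extra assessments works only once someone already suspects an event.

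**Conclusion.** The point holds for infusion 3. Between the 24-hour call and the 6-month visit, about 161 to 203 days, no scheduled contact asks about adverse events in any of up to 24 patients. The remainder of the protocol's event window and the last four Lovenox days both fall in that interval. The likely consequence is under-recording or misdating of lower-grade events, which weakens the primary safety assessment. How many events would be lost cannot be estimated from the documents. For infusions 1 and 2 the issue is a delay of 10 to 16 days, not an absence of ascertainment.

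This is a worthwhile, inexpensive improvement rather than a flaw that invalidates the design. Confidence is medium: it rests on the visible text and Tables 1a/1b being complete on scheduled contacts. Separately, the 4-hour and 48-to-72-hour windows for Grade 4-5 CNS events contradict each other and must be reconciled. This review does not say which should stand.

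**What to change.** Amend the Synopsis, section 3.6 and footnote 8 of Tables 1a and 1b. Keep the 24-hour call and add:

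1. a scripted adverse-event call after each infusion, once the protocol's event window has closed; it is most needed after infusion 3;
2. a scripted call about 14 days after infusion 3, with VTE and bleeding questions, matching the interval at which infusions 1 and 2 are followed up;
3. for both, participation of the caregiver or LAR where the subject cannot report reliably.

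Reconcile section 4.3 with stopping rule 3 and state plainly what 48 to 72 hours means, since call 1 is timed from it.

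The calls change data collection only; treatment and stopping thresholds are untouched. They do not replace an examination or laboratory tests, so infusion 3 would still be followed less closely than infusions 1 and 2.

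Cost: 24 × 3 = 72 calls for item 1 plus 24 for item 2, at most 96. If item 1 is limited to infusion 3, the total is 24 + 24 = 48. Separate conversations with caregivers could at most double the number (2 × 96 = 192). A short amendment is also needed.

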6. SAFETY MONITORING AND REPORTING PLAN

The study will be conducted according to Good Clinical Practice (GCP) guidelines, the Declaration of Helsinki, US 21 Code of Federal Regulations (CFR) Part 50 – Protection of Human Subjects, and Part 56 – Institutional Review Boards. An independent Medical Safety Monitor (MSM), monitors from an Independent Contract Research Organization (CRO) and a Data Safety Monitoring Board (DSMB) will provide study oversight.

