7. SUBJECT WITHDRAWAL

7.1 Description of Subject Completion

Subjects are considered to have completed the study if they completed three HB-adMSC fusions and the follow-up study visits at 6 and 12 months and the two year post-infusion telephone interview.

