7.2 Withdrawal of Individual Subjects

The research team will make every reasonable effort to keep each subject in the study through the two year end of study telephone interview. If a subject withdraws from the study, the reason for withdrawal will be documented in the study records. Possible reasons for withdrawal include: adverse experiences, protocol non-compliance, lost to follow-up, at the discretion of investigator, the DSMB, the study sponsor, or other regulatory agencies. Study data and biological samples collected up to the point of withdrawal will remain in the study database for analysis.

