7.3 Withdrawal of Subject from the Study Following Adverse Events

The PI will determine if an adverse event (AE) is of sufficient severity to require stopping subject participation. The subject (or LAR) may also voluntarily withdrawal from the study due to what he/she perceives as an intolerable AE. If the withdrawal from the study is due to an AE, the subject will be offered appropriate care under medical supervision until the symptoms of the AE resolve or the subject's condition becomes stable. Subsequent review by the MSM, DSMB, IRB or the study sponsor may also result in the suspension of further enrollment.

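### Meeting a stopping rule automatically stops enrollment only; holding the infusions still due to subjects already in the study is left to discretion

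*Protocol*

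**What the plan says.** The Synopsis lists four stopping rules under one lead sentence: "The stopping rules listed below will trigger cessation of enrollment and potential study closure pending a comprehensive DSMB safety review". In brief, the rules are an infusion-related death; infusion-related sustained hypoxia or new mechanical ventilation; a Grade 4-5 cerebrovascular ischemia or seizure event within 48 to 72 hours of an infusion; and any Grade 4-5 event that the Medical Safety Monitor and/or DSMB judges temporally related to an infusion.

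Three other places bear on who may stop dosing:

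- Section 6 names an independent Medical Safety Monitor and says that "a Data Safety Monitoring Board (DSMB) will provide study oversight".
- Section 7.2 lists, among possible reasons for withdrawing an individual, withdrawal "at the discretion of investigator, the DSMB, the study sponsor, or other regulatory agencies".
- Section 7.3 says "The PI will determine if an adverse event (AE) is of sufficient severity to require stopping subject participation", and then "Subsequent review by the MSM, DSMB, IRB or the study sponsor may also result in the suspension of further enrollment".

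Section 3.6 schedules three infusions per subject at 14-day intervals with a 3-day window either side. Table 1a places a period headed "5 to 7 weeks for HB-AdMSC Processing" before the first infusion. Section 3.4 refers to a staggered infusion plan for the first four subjects in Appendix 3.

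**The concern.** The exposure that each rule guards against is the infusion, but the automatic response acts on entry to the study. In a single-dose trial the two nearly coincide. Here they do not: a subject can be enrolled with up to three infusions still to come.

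Infusional toxicity is the primary objective, and Sections 1.1 and 4.1 describe a pro-coagulant hazard of the cell type that could apply to more than one subject. After an infusion-related death or Grade 4-5 event, the people already scheduled for further doses are those most directly exposed to a repeat. A stopping rule exists so that their protection does not depend on someone deciding in time. The rule as worded gives that protection to people not yet enrolled, and gives it to no one once enrollment is complete.

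**Working it through.** The plan gives no figure to reproduce. The check is a comparison of texts, plus the dosing calendar.

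**1. What each provision does when a rule is met**

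| Place | Acts on | Automatic? |
|---|---|---|
| Synopsis, Stopping Rules, first part | Enrollment | Yes |
| Synopsis, Stopping Rules, second part | Whole study (closure) | No, *potential* |
| Section 3.6, infusion visit steps | Checks of patient, consent, procedure and cell product | No check for a triggered rule and no criteria for holding a dose |
| Section 6, opening paragraph | General oversight | No specific action stated |
| Section 7.2 | An individual subject | No, discretionary |
| Section 7.3, first sentence | The subject with the event | No, investigator's judgment |
| Section 7.3, last sentence | Enrollment again | No, *may* |

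No row is both automatic and directed at dosing across the study.

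**2. What falls due after a trigger**

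Inputs from Section 3.6: nominal interval 14 days, window 3 days either side, three infusions. Take day 0 as the day a rule is met, and consider a subject given infusion 1 that day.

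- Infusion 2: 14 − 3 = 11 to 14 + 3 = 17, so day 11 to 17.
- Infusion 3, with the window applied to each interval in turn: 2 × 11 = 22 to 2 × 17 = 34, so day 22 to 34 (nominally 2 × 14 = 28).
- If the window is instead read as 3 days around the nominal date, infusion 3 is due at 28 − 3 = 25 to 28 + 3 = 31, which lies inside the same range.

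A subject given infusion 2 on day 0 is due infusion 3 on day 11 to 17.

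**3. Subjects not yet dosed**

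The available text does not define when a subject counts as enrolled. If that point is consent or tissue extraction, a subject in cell processing (5 × 7 = 35 to 7 × 7 = 49 days) is already enrolled, and a stop to enrollment does not reach infusion 1 either. If the point is the first infusion, this group is held and only infusions 2 and 3 are outside the automatic action.

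**4. After the last enrollment**

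With all 24 subjects enrolled there is no enrollment left to stop. Only the potential closure and the discretionary powers remain, while the last subjects may still have infusions due.

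**The case against.** The strongest reply is that nobody would go on dosing after such an event. The investigator, sponsor and DSMB can each withdraw subjects. An independent Medical Safety Monitor is in place, and the fourth rule is met only once that monitor or the DSMB has judged the event, so an oversight body is already engaged. This stands in part: the protocol provides the means to stop dosing, and a prompt decision is likely. What it does not provide, in the text available, is a hold that applies without a decision.

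A second reply is that the evidence is incomplete. The quoted rule comes from the Synopsis, only the opening paragraph of Section 6 was available, and Appendix 3 and any DSMB charter were not. These are natural places for a dosing hold. This stands as a limit on the conclusion. Even if a hold exists there, the Synopsis sentence names only enrollment and should agree with it.

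Three stronger readings are tempting, and the documents do not support them:

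- *That the protocol makes continued dosing the default during review.* The rule is silent on dosing. Nothing directs infusions to go ahead after a trigger.
- *That closure can come only after the DSMB review.* The word *pending* can also mean closure while the review is awaited. Closure is not automatic on either reading, but its timing should not be asserted.
- *That a given number of infusions would be at risk.* That needs accrual and review length, and neither is stated. With slow accrual, courses may not overlap, and the only infusions due could belong to the affected subject, whom Section 7.3 already covers by the investigator's decision.

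**Conclusion.** The point holds as a cheap improvement to a stated rule. Followed literally, the rule stops entry and leaves the exposure behind all four triggers to discretionary decisions. Its size is best given by the calendar: infusions 2 and 3 come due 11 to 17 and 22 to 34 days after infusion 1, and the automatic action reaches neither. No study-level count is claimed.

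The conclusion rests on two conditions: that *enrollment* carries its ordinary meaning of entry to the study, so that someone already dosed is enrolled; and that no hold exists in the parts of the protocol, its appendices or a charter that could not be read. If a hold is found there, the point reduces to making the Synopsis consistent with it.

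**What to change.** Replace the lead sentence of the Stopping Rules with: *Any of the following will immediately suspend enrollment and all further HB-adMSC infusions in all subjects until the DSMB completes its safety review and authorizes resumption; safety follow-up continues.*

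Add one sentence: *At resumption the DSMB decides whether doses that have passed their 14 ± 3 day window are given late or omitted.*

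Carry the same wording into Section 6. If Section 6, Appendix 3 or a charter already contains a hold, cite it and bring the Synopsis sentence into line.

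The drafting cost is a two-sentence amendment and a consistency check. The operating cost is that some infusion windows or prepared autologous cells may be lost during a hold. A subject whose dose is omitted would not meet Section 7.1, where "Subjects are considered to have completed the study if they completed three HB-adMSC fusions" and the later follow-up. Because the fourth rule covers any temporally related Grade 4-5 event, a laboratory abnormality of that grade could also trigger a hold; the DSMB can lift it quickly.
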